the Drinking Inventory of Consequences (DrInC) to assess interpersonal, physical, social, impulsive, and intrapersonal consequences of alcohol use, and the Daily Drinking Questionnaire (DDQ) to assess quantity/frequency of alcohol use over the previous week to look at self-report changes in drinking. Similarly, at baseline, weekly and follow-up we will administer the Posttraumatic Diagnostic Scale (PDS) to assess for ongoing PTSD symptoms and change in PTSD symptoms. Finally, at baseline and 3-months we will administer self-report measures to assess functioning and change in functioning including drug use, depression, and treatment received. Finally, a post-study reactions questionnaire will be given at the last weekly intervention session to assess participant reactions to the assessment and intervention strategies. This measure will be used to assess the feasibility and acceptability of the intervention.

Assessment and Intervention Training: Study assessors will be trained to administer interview assessments of PTSD and alcohol use and self-report measures, by receiving group didactics on interview measures and doing role plays of conducting interview assessments. They will complete at least one mock assessment before beginning assessments. The assessors will meet weekly as a group to discuss and make inclusion decisions and minimize rater drift and will receive as-needed supervision on assessment techniques. Interventionists will also be trained in the 90-minute in-person intervention and coaching calls. Intervention training will consist of group didactics, role plays, and mock interventions. Interventionists will participate in ongoing weekly group supervision. Fidelity to the intervention and reliability of assessments will be calculated for a subset of the sample once data collection is complete.

Procedures: Study procedures will begin with phone screening with the research coordinator (RC) to determine initial eligibility for SA exposure, PTSD symptoms, and alcohol use.

Potentially eligible individuals will be scheduled for an in-person baseline session.

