This study involves 7 assessment time-points: baseline, at intervention or post-randomization (for the AO group), 4 weekly assessments, and 3-month follow-up assessment. The baseline session will last 1.5-2 hours and will consist of interview (PSS-I, TLFB, SCID modules) and self-report measures on SA (SES), PTSD (PDS), depression/suicide (BDI), and substance use (DDQ, DrInC, DUDIT,). Baseline will be conducted by an assessor, and at the conclusion the RC will inform the participant of randomization condition (intervention vs. AO). Participants will be randomized with their condition known only to the RC and the PI, while the assessor who conducts baseline assessments will remain masked to condition. At baseline participants will be compensated at a rate of \$20/hour. One week after baseline, individuals randomized to the intervention will return and meet with a interventionist for a 90 minute in-person intervention. At that time they will complete self-report measures on drinking and PTSD and will be compensated \$10 for completing the questionnaires (PDS, DDQ, DrInC). One week following baseline AO participants will log on to a secure web server, complete these same measures of PTSD and drinking behavior, and be compensated \$10. For the next 4 weeks, intervention participants will complete weekly 15-minute coaching calls with their assigned interventionist. Prior to each coaching call they will be prompted to complete on-line self-report measures of PTSD and alcohol use (PDS, DDQ, DrInC). AO participants will complete these same measures weekly without the coaching call. Participants will receive \$10 for each on-line assessment they complete; those who complete all 4 will receive a \$20 bonus. Finally, participants will be assessed at 3-month follow-up. They will meet with the same assessor from baseline and will recomplete interviews of PTSD and alcohol use, and self-report measures of alcohol and drug use, PTSD, depression, treatment satisfaction (reaction to treatment) and treatment received (Form 90). At 3-month follow-up participants will be paid \$25/hour.

Participant Retention. We will use strategies including reminder calls/texts, weekly check in calls during active treatment for both groups, increasing incentives for follow-ups, and bonus payments for full completion to achieve an expected 80% retention rate.

Power and Data Analytic Plan.

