Data analytic plan. Prior to inferential statistics, scale scores will be calculated for each of the variables following previously validated procedures. Univariate and bivariate descriptive statistics will be used to assess distributions and simple relationships among study variables. We will examine factors such as completion rate, number and length of coaching calls completed, and participants' reaction to treatment (reaction to treatment) to examine the feasibility of the intervention.

Preliminary Analyses

Stata 15.1 (StataCorp, 2017) was used for all analyses. Potential differences by treatment condition in demographics and background characteristics including age, race, ethnicity, sexual orientation, and treatment history were examined with *t*-tests or chi-square tests.

Primary Analyses

First, we will examine intervention satisfaction and acceptability by means and standard deviations of each satisfaction rating. Next, to evaluate differences between BRITE and the symptom monitoring control condition in PTSD and alcohol use outcomes between baseline and 3-month follow-up, we will conduct separate multilevel mixed-effects models for PTSD symptom severity, average drinks per drinking day, heavy episodic drinking frequency, and alcohol consequences. We will fit two-level random-intercept models with an independent covariance structure between the random effects controlling for treatment history testing for a condition x time interaction. We will conduct similar multilevel mixed-effects models examining

differences between BRITE and AO in PTSD symptom severity, average drinks per drinking day, and heavy episodic drinking frequency using self-reports at baseline, randomization (also intervention delivery session), each of the four weeks of coaching calls, and the 3-month follow-up controlling for treatment history. Pairwise comparisons for intervention x time effects were examined as described above.

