Missing data. For missing data, we will examine both intent-to-treat and completer analyses to examine possible differences in the outcome as a result of drop out. For missing data due to a participant providing incomplete data, we will examine whether the missingness can be considered ignorable (e.g., missing completely at random or related to variables in the analyses [including earlier time points]). For any non-ignorable missing data, we will use multiple imputation procedures or employ analytic procedures that handle missing data in less biased ways such as maximum likelihood estimation.

Power analysis. The RCT was powered to examine the main hypothesis regarding the efficacy of the intervention compared to AO on PTSD and drinking. We expect a medium-to-large effect size for both alcohol and PTSD outcomes Using G*Power 3.1.7 with an ANOVA with 3 repeated measures, a sample size of 60 (30 per condition) is needed to identify medium-to-large effects with power of .80. To obtain this sample of treatment completers, we will recruit 76 women (38 per condition).

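### The main two-wave models use only baseline for a woman who misses the 3-month visit; with the weekly scores left out, the estimate can be biased if dropout follows early response differently by arm

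*Combined protocol and SAP*

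**What the plan says.** Under Primary Analyses, the main models are fitted "to evaluate differences between BRITE and the symptom monitoring control condition in PTSD and alcohol use outcomes between baseline and 3-month follow-up". They are two-level random-intercept models, adjusted for treatment history and tested by the condition-by-time interaction. The outcomes are PTSD severity, drinks per drinking day, heavy episodic drinking and alcohol consequences.

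The Procedures section lists seven assessment points, so five lie between baseline and 3 months. PDS, DDQ and DrInC are completed at all five in both arms. The Measures section says of the PTSD scale: "at baseline, weekly and follow-up we will administer the Posttraumatic Diagnostic Scale (PDS"). Primary Analyses sends these waves to a second set of self-report models for PTSD severity, drinks per drinking day and heavy episodic drinking. Alcohol consequences is not in that set.

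The Missing data section plans intent-to-treat and completer analyses to look at dropout. For incomplete data it asks whether missingness is ignorable, meaning "missing completely at random or related to variables in the analyses [including earlier time points". Multiple imputation or maximum likelihood is reserved for missingness found non-ignorable, and no imputation variables are named. Participant Retention describes measures "to achieve an expected 80% retention rate".

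**The concern.** A likelihood model protects against dropout that depends on data inside the model. In the two-wave models that means baseline, arm and treatment history. A plausible driver of missing the 3-month visit is how PTSD and drinking went over the preceding weeks. The weekly forms measure this, but the main models do not contain it. Dropout that is ignorable given the weekly scores is then not ignorable in the model actually fitted.

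At stake is the main efficacy estimate. If, for example, women who are not improving leave the coached arm while dropout in the assessment-only arm is unrelated to response, the intervention looks better than it is. If improvers leave the coached arm instead, it looks worse.

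The stated remedy does not clearly close the gap. Standard multiple imputation and maximum likelihood assume ignorable missingness, so invoking them only when missingness is judged non-ignorable reverses their role. The main mixed models are normally fitted by likelihood already, so that option adds nothing unless the weekly scores enter.

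**Working it through.** **The plan's own figures.** Power analysis: "a sample size of 60 (30 per condition) is needed to identify medium-to-large effects with power of .80", then "we will recruit 76 women (38 per condition"). With 80% retention, 30/0.80 = 37.5, so 38 per arm and 76 in all; 76 x 0.80 = 60.8. The 20% loss is therefore the plan's own figure. The 60 is nearly reproduced by a between-groups test with three measures (power 0.799 at f = 0.30, correlation 0.5, two-sided alpha 0.05). Those three inputs are assumed, and this point does not rest on them.

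**Inputs for the bias.** From the documents: 38 per arm, 20% missing at 3 months, two waves in the main model. Assumed, because the documents give none: all scores in SD units; correlation of baseline with 3 months r03 = 0.4-0.5; of the last weekly score W (about week 5) with 3 months rW3 = 0.6-0.8; of baseline with W, r0W = 0.5 (used in the hand calculation); dropout log-odds rising by 1 per SD of W; higher scores worse.

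**Hand calculation, one arm.**

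1. Dropout probability is 1/(1 + exp(-(a + W))) with W standard normal. A 20% loss requires a = -1.65 (numerical integration).
2. The mean of W is then +0.693 in leavers and -0.173 in those observed. Check: 0.2 x 0.693 - 0.8 x 0.173 = 0 to rounding.
3. The two-wave likelihood estimate of the 3-month mean is (observed 3-month mean) + r03 x (baseline mean of all - baseline mean of those observed).
4. Its bias is -0.173 x (rW3 - r03 x r0W). At r03 = 0.5, r0W = 0.5, rW3 = 0.7: -0.173 x (0.70 - 0.25) = -0.078 SD.
5. Range: rW3 = 0.6 with r03 = 0.5 gives 0.173 x 0.35 = 0.061; rW3 = 0.8 with r03 = 0.4 gives 0.173 x 0.60 = 0.104.
6. If the other arm has the same mechanism and no true effect, the two biases cancel. If it runs the opposite way they add: 2 x 0.078 = 0.156 SD, range 0.12-0.21.

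**Simulation of the two-wave model, 20% missing.** The first bias column has dropout following the last weekly score (38 per arm, no true effect). The other columns have it following early change (baseline with 3 months 0.5; last weekly score with 3 months 0.6 or 0.7). Type I error and coverage are for N = 76, the stronger correlation and no true effect.

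| Dropout depends on early response | Bias, weekly score (SD) | Bias, early change (SD) | Type I error | 95% CI coverage |
|---|---|---|---|---|
| Not at all | about 0 | 0 | .050 | .950 |
| Same way in both arms | about 0 | 0 (no effect) to 0.03 (effect 0.6 SD) | .052 | .948 |
| Intervention arm only | 0.07-0.09 | 0.05-0.10 | .067 | .933 |
| Opposite directions by arm | 0.14-0.18 | 0.12-0.16 | .096 | .904 |

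Under the weekly-score mechanism, type I error with opposite directions was 8-12%. The standard error of the estimate is about 0.25 SD, so the one-arm bias is 0.07/0.25 to 0.09/0.25, or 0.28-0.36 standard errors. The opposite-direction bias is 0.56-0.72.

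**Effect of using the weekly data.** Adding the last weekly score, by likelihood or by a small arm-specific imputation, cut the bias to about 0.01 SD or less and slightly improved precision (standard error down 1-5% in the likelihood version). This assumes the weekly scores are observed.

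**Intent-to-treat against completers.** Taking completers as women seen at 3 months, the two estimates correlate 0.96-0.97. In step 4 the completer change has bias -0.173 x (rW3 - r0W) = -0.173 x 0.20 = -0.035, smaller than -0.078. When dropout follows change instead, completers are further off (0.133 against 0.088 SD; one arm, stronger correlation, no true effect). A gap between the two analyses therefore does not show which is nearer the truth.

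**The case against.** Four points on the other side have weight.

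- **Multiple imputation is allowed.** The plan does not restrict its variables, and the plural reference to variables in the analyses could cover the weekly waves. A reader might infer that the plan has decided to ignore these data; no passage says so. What stands is that the weekly scores are not named, the trigger is the wrong way round, and an imputation model left open can be chosen after results are seen.
- **The seven-wave models use the weekly data.** A woman who leaves late informs their 3-month contrast through her weekly scores. This is a real partial check for three outcomes. It is not designated to correct the main estimate, and alcohol consequences has no such model although DrInC is collected weekly.
- **The bias is conditional.** A reader might infer that dropout linked to early response biases the main result outright. It does not: the mechanism has to differ by arm for more than about 0.03 SD. The documents report no such difference, and they plan check-in calls in both groups and the same payment per form. On the other hand, one arm has a 90-minute session and coaching calls while the other only completes forms, so different reasons for leaving are plausible.
- **Weekly data may be missing too.** A reader might assume five waves for every woman lost. Early leavers may have few or none, and the first of the five is taken at the intervention session, so only four clearly follow it.

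It would also go too far to say that comparing intent-to-treat with completer results cannot reveal a problem. The two can differ; the comparison is weak because it neither identifies the cause nor gives a corrected estimate. Nor are all the main outcomes interview-based: the DrInC is self-report, and Primary Analyses names no instrument for the main set.

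**Conclusion.** The point holds as a conditional risk with a cheap remedy. The main estimate uses only baseline for a woman without a 3-month visit, and the plan does not assign the weekly scores to her missing outcome. At 20% loss the resulting bias is about 0.07-0.09 SD if dropout follows early response in one arm only and 0.14-0.18 SD if in opposite directions. It is negligible if dropout is random or works alike in both arms. In the one-arm case this is about a third of a standard error, with type I error near .067: modest, but avoidable. Only the sample size and the loss come from the documents; the correlations and the strength and form of the dropout mechanism are assumed. The change is worth making before analysis, but the documents do not show that the result will be biased.

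**What to change.** State in the Missing data section that the intent-to-treat analysis of all four 3-month outcomes will, by default, use multiple imputation by arm, or an equivalent joint likelihood model. Auxiliaries should be a small named set, such as the last available or mean weekly PDS, DDQ and DrInC score. Remove the condition that these methods apply only when missingness is judged non-ignorable. Keep the plain two-wave model as a sensitivity analysis, and add a not-at-random sensitivity analysis for dropout that the weekly scores do not explain.

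The cost is SAP wording and modest programming, with no new data collection. With about 30 observed women per arm the imputation model must stay small; a version carrying every weekly score and form count has not been tested here. Women who leave before giving weekly data gain little from it.

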Developing a brief early cognitive intervention for PTSD and alcohol misuse

NCT02808468

03/08/2014

Study Protocol

This study is a small pilot randomized controlled trial (RCT) to test initial efficacy of a one session + four coaching call cognitive intervention compared to symptom monitoring for the reduction of PTSD and alcohol use following a recent sexual assault (SA). Participants will be assessed at baseline, randomly assigned to receive the intervention plus weekly assessments vs. weekly assessments only (AO), and assessed again at 3-month follow-up.

Recruitment and Participants: Participants are recruited via community advertisements (flyers, online) and specific outreach targeted toward female identifying students enrolled at the first author's institution. We will collaborated with local community organizations to receive referrals.

Participants will be 76 (n = 38 intervention, n = 38 AO) women who are 2-10 weeks post SA and report alcohol misuse and PTSD symptoms. We will restrict our sample to women given that the majority of SA victims are female and the pilot nature of this study. For this research, SA will be defined as any non-consensual sexual activity ranging from forced penetration to unwanted contact. Participants will need a minimum of subthreshold PTSD symptoms related to recent SA (specifically criteria for two of the three PTSD symptom clusters; 1 reexperiencing, 3 avoidance, 2 hyperarousal) to ensure that they are experiencing SA related distress. Participants will endorse hazardous drinking over the past month, defined as exceeding NIAAA recommendations for low risk drinking for women (more than 3 drinks on one occasion) and at least two negative consequences of drinking. Additional inclusion criteria include: 1) female gender; 2) age \geq 18 years, 3) capacity for informed consent, 4) English fluency, 5) no planned absences that would interfere with 5 weeks of participation, and 6) access to a telephone. Individuals will be excluded if they are 1) acutely suicidal with intent/plan or 2) exhibit current

psychosis.

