Measures. Below is a description of measures for each time point. Phone Screening. To initially assess for SA exposure, we will include 2 questions on nature and timing of assault. We will also include a 20-item PTSD screen to assess that participants meet at minimum subthreshold PTSD symptoms. Finally, we will ask 2 items that assess quantity and frequency of drinking, and one to determine if alcohol has caused any problems in the previous week to ensure likelihood of hazardous drinking. *Interview Measures*. At baseline interviews are administered including the mood and psychotic disorder modules of the Structured Clinical Interview for DSM-IV (SCID) at baseline to assess for exclusion criteria of current psychosis or acute suicidality. At baseline and 3-month follow-up, we will administer the Timeline Followback (TLFB), a calendar based assessment of drinking with established reliability, to assess for quantity and frequency of alcohol use for the prior month. This will enable us to assess drinking at baseline and change in drinking following the intervention. Finally, at baseline and 3month follow-up we will administer the Posttraumatic Stress Symptom Scale- Interview version (PSS-I) to assess for both DSM-IV diagnostic criteria of PTSD and severity of symptoms over the past two weeks. The PSS-I has excellent reliability and validity and will assess for change in PTSD symptoms with the intervention. Self-report Measures. We will administer self-report measures of drinking, assault history, and psychopathology at the in-person baseline and 3month assessments and a briefer subset of these measures will be administered online at weekly intervals for four weeks following baseline. All self-report measures are widely used and have established reliability and validity. Constructs that are assessed include demographic information to describe the sample (e.g., age, race), history of unwanted sexual experiences, alcohol measures at baseline, weekly assessments, and 3-month follow-up to assess drinking behavior,

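### The stated .80 power at 60 completers is for a three-wave ANOVA, but the planned analyses have two or seven waves, so the figure does not describe the planned test

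*Combined protocol and SAP*

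**What the plan says.** The Power analysis paragraph says the trial was powered for its main hypothesis, efficacy against assessment only on PTSD and drinking. It bases the sample size on this: "Using G*Power 3.1.7 with an ANOVA with 3 repeated measures, a sample size of 60 (30 per condition) is needed to identify medium-to-large effects". The stated power is .80. It then recruits 76 women, 38 per condition, to end with that number of completers. The effect size is given in words only.

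The analyses are laid out elsewhere:

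- **Study Protocol, opening paragraph.** Participants are assessed at baseline, randomized to the intervention plus weekly assessments or to "weekly assessments only (AO), and assessed again at 3-month follow-up".
- **Primary Analyses, first set of models.** These compare the arms "in PTSD and alcohol use outcomes between baseline and 3-month follow-up", for PTSD severity, drinks per drinking day, heavy episodic drinking frequency and alcohol consequences, "controlling for treatment history testing for a condition x time interaction".
- **Primary Analyses, second set of models.** These are similar models "using self-reports at baseline, randomization (also intervention delivery session), each of the four weeks of coaching calls, and the 3-month follow-up".
- **Measures, Interview Measures.** "at baseline and 3month follow-up we will administer the Posttraumatic Stress Symptom Scale- Interview version (PSS-I"), and "At baseline and 3-month follow-up, we will administer the Timeline Followback (TLFB").
- **Procedures.** "This study involves 7 assessment time-points".

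**The concern.** A power figure is useful only if it refers to the test that will be run. Here the calculation has three repeated measures, while the first set of outcome models has two and the second has seven. The two interview measures cannot supply a third wave, because each is given only at baseline and 3 months.

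This is the only sample-size justification in the documents. If the condition-by-time result is null, .80 is the figure a reader would use to judge how informative that null is, and it belongs to a design the trial does not have. The inputs that would let a reader translate it to the planned test are not given.

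**Working it through.** **1. Count the waves.** Power calculation: 3. First outcome models: 2 (baseline, 3 months). Self-report models: 1 baseline + 1 randomization/intervention session + 4 weekly + 1 at 3 months = 7, which agrees with the seven time-points in Procedures. None has 3.

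**2. Inputs.**
- Stated: G*Power, ANOVA, 3 measures, 60 completers (30 per arm), power .80, a verbal effect size, 80% expected retention (Participant Retention) and 76 recruited.
- Not stated: alpha, a numerical effect size and its metric, rho, any sphericity correction, and whether the between-groups or the interaction term was tested.
- Assumed below: two-sided alpha 0.05, rho 0.3 to 0.7, sphericity, a continuous outcome with equal SDs at both waves, no covariate, and both waves observed for all 60.

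**3. Try to reproduce N=60 with m=3 waves and 2 groups, assuming f=0.30.**
- Between-groups term: λ = N f² m / (1 + (m−1)rho), df 1 and N−2. At rho 0.5, λ = 60 × 0.09 × 3 / 2 = 8.1, giving power .799 at N=60. The smallest equal-arm N reaching .80 is 50, 62 and 72 at rho 0.3, 0.5 and 0.7.
- Condition-by-time term: λ = N f² m / (1 − rho), df 2 and 2(N−2). The smallest N is 28, 20 and 14 at the same rho values.
- Condition-by-time term with f derived from partial eta-squared: λ = f² × 2(N−2). The smallest N is 58, with power .82 at N=60.

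So 60 is a plausible output under more than one reading, but the same verbal description also fits required sizes from 14 to 72.

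**4. Power for the planned two-wave condition-by-time test.** With complete pairs this is a two-sample test on change scores. Let d be the between-arm difference in change divided by the outcome SD: λ = d² n / (4(1 − rho)), n = 30 per arm, df 1 and 58. For example, d=0.50 and rho 0.3 give λ = 0.25 × 30 / 2.8 = 2.68 and power .36. In ANOVA terms λ = N f² × 2 / (1 − rho); equating the two with N = 2n gives d = 4f.

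| Effect | rho 0.3 | rho 0.5 | rho 0.7 |
|---|---|---|---|
| d=0.50 (f=0.125) | .36 | .48 | .69 |
| d=0.80 (f=0.20) | .73 | .86 | .98 |
| f=0.25 (d=1.00) | .90 | .97 | .998 |

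The effect detectable with 80% power is d = 0.87, 0.74 and 0.57 at rho 0.3, 0.5 and 0.7. Dividing by √(2(1 − rho)), the SD of a change score in outcome-SD units, gives 0.74 change-score SDs at every rho.

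**5. Carry the same f from three waves to two, at N=60.**
- Interaction term: f = 0.196, 0.166 and 0.128 (rho 0.3, 0.5, 0.7) give .80 with three waves. With two waves each gives power of about .71.
- Between-groups term: f = 0.269, 0.300 and 0.329 give .80 with three waves, and .72, .75 and .78 for the same term with two.
- The between-groups f values entered for the two-wave interaction instead give .93 to above .99.

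**6. Recruitment.** 60 / 0.80 = 75, or 76 for equal arms. This step is correct.

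**The case against.** The best defence is that the plan's sentence may well be true of the planned test. With 30 per arm the two-wave test has 80% power for 0.74 change-score SDs, which lies between the conventional medium (0.5) and large (0.8) standardized differences. In outcome-SD units the detectable d is 0.80 or less once rho is about 0.41 or more. In G*Power's own metric, a conventional medium f of 0.25 gives two-wave power of .90 or higher. This stands. It rules out calling the trial underpowered, and it means a low figure such as .36 should not be shown without the f=0.25 results.

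It is also fair that 60 can be produced by plausible inputs, that no arithmetic error has been shown, and that this is described as a small pilot of initial efficacy. The Data analytic plan is partly in the past tense, so the gain may be only a later correction of wording. These points limit the severity. They do not remove the mismatch: the plan makes an explicit power claim for its main hypothesis and ties it to a number of waves that no analysis has.

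A reader might infer two stronger things. One is that the trial is too small; the documents give no alpha, rho or numerical effect from which that could follow. The other is that the authors powered a between-groups effect averaged over waves, because f=0.30 with rho 0.5 gives .799. That match is suggestive only, since the partial eta-squared interaction comes equally close.

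**Conclusion.** The point holds as a mismatch between the power model and the analysis model, with incomplete reporting of inputs. Its severity is minor to should-fix. The .80 belongs to a three-wave ANOVA, and the documents do not show whether power for the two-wave condition-by-time test is above or below it.

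The size of the uncertainty depends on the effect-size metric and rho as much as on the number of waves, as the table shows. The one like-for-like comparison, moving a fixed interaction f from three waves to two, lowers .80 to about .71. All of this rests on the assumptions listed in the working. The continuous, equal-SD assumption is unverified for drinks per drinking day, heavy episodic drinking frequency and alcohol consequences. The calculation also leaves out the treatment-history covariate and any contribution from non-completers under the intent-to-treat analysis. It says nothing about the seven-wave models.

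**What to change.** Keep 60 completers and 76 recruited. Replace the three-repeated-measures sentence with power for the two-wave condition-by-time test, stating alpha, one planning value of rho and the effect-size metric. Possible wording, to be cut to the chosen rho:

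> 30 completers per arm, two waves, two-sided alpha 0.05: 80% power for a between-arm difference in change of 0.74 change-score SDs (0.87, 0.74 or 0.57 outcome SDs at rho 0.3, 0.5 or 0.7).

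Add that this assumes continuous outcomes with equal SDs at both waves, that this is unverified for the drinking outcomes, and that it does not cover the seven-wave models. Use planning values, not observed results. If data have already been analysed, label the restatement as made afterwards.

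The cost is wording only, with no added participants, outcomes or analyses. The downside is that the restated figure may be less favourable than .80.
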